#### **2.1.4.3 Laboratory safety variables**

Clinical laboratory data consists of blood analysis, including hematology, and clinical chemistry. Clinical laboratory values after conversion will be analyzed into standard international units and international units will be used in all listings and tables, unless otherwise specified.

Blood samples for clinical laboratories will be taken as described in the study flow chart in the protocol. The laboratory parameters will be classified as follows:

- Hematology
  - **Red blood cells and platelets:** hemoglobin, hematocrit, red blood cell count, platelet count;
  - **White blood cells:** white blood cell count, neutrophils, lymphocytes, monocytes, basophils, eosinophils.
- Clinical chemistry
  - **Metabolism:** fasting plasma glucose, total protein, albumin, creatine phosphokinase (CPK);
  - **Electrolytes:** sodium, potassium, chloride;
  - **Renal function:** creatinine, uric acid, estimated glomerular filtration rate (eGFR);
  - **Liver function:** alanine aminotransferase (ALT), aspartate aminotransferase (AST), alkaline phosphatase (ALP), gamma glutamyl transferase ( $\gamma$ GT), lactate dehydrogenase (LDH), total bilirubin;
  - **Hepatitis screen:** anti-hepatitis-C antibody.

Technical formulas are described in [Section 2.5.1](#).

#### **2.1.4.4 Vital signs variables**

Vital signs include: weight, heart rate, systolic and diastolic blood pressure in the sitting position.

#### **2.1.5 Other endpoints**

Other assessment endpoints defined below are exploratory.

##### **2.1.5.1 HbA1c**

The absolute change in HbA1c (%) from baseline over time: same definitions and rules as for normalized TAV (see [Section 2.1.3.1](#)).

##### **2.1.5.2 hs-CRP**

The percent change in hs-CRP from baseline at Week 36 is defined using same definitions and rules as for normalized TAV, when applicable (see [Section 2.1.3.1](#)). hs-CRP values greater or equal to 10 mg/L will be excluded from analyses in a second approach, since these are suggestive of concurrent infections, MI, or other events provoking an acute phase response ([3](#)).

PCSA criteria for hs-CRP are defined in [Appendix A](#).

##### **2.1.5.3 Patients with LDL-C <25 mg/dL (0.65 mmol/L)**

The assessment will include:

- The proportion of patients with two consecutive results, spaced out by at least 21 days, of LDL-C <25 mg/dL (<0.65 mmol/L) (respectively LDL-C <15 mg/dL, ie, <0.39 mmol/L) during the treatment period
- The time to the first LDL-C <25 mg/dL (respectively LDL-C <15 mg/dL) for these patients.

Only calculated LDL-C will be used for this endpoint.

#### **2.1.6 Quality-of-life endpoints**

EQ-5D is a standardized and generic instrument for measuring the health status and health related quality of life (QOL) for clinical and economic assessment ([4](#)). EQ-5D instrument includes 5 items corresponding to the following dimensions: mobility, self-care, usual activities, pain/discomfort, anxiety/depression ([Appendix B](#)). Each item can take 1 of 3 responses: (1.) “no problem”, (2.) “some problems”, and (3.) “severe problems”. Overall health status is defined as a 5-digit number and will be converted into a standard utility score ranging between -0.111 (representing severe problems) and 1 (representing no problem): the single index utility score, using a regression model ([, Appendix C](#)). If response to one or more dimension is missing, the utility score will be missing.

QOL parameters include response to each EQ-5D items and change in utility score over time from baseline.

## 2.2 DISPOSITION OF PATIENTS

This section describes patient disposition for both patient study status and the patient analysis populations.

Included population consists of the patients who signed the informed consent.

Randomized patients consist of all patients who have been randomly allocated to a treatment group and recorded in the registration center, regardless of whether the study drug was used or not. Patients treated without being randomized will not be considered as randomized and will not be included in any analysis population.

For patient study status, the total number of patients in each of the following categories will be presented in the clinical study report using a flowchart diagram or summary table:

- Patients who signed the informed consent
- Non-randomized patients and reasons for non-randomized, if any;
- Non-randomized but treated patients, if any
- Randomized patients
- Randomized but not treated patients and reason for not being treated;
- Randomized and treated patients
- Patients who did not complete the study treatment period as per protocol;
- Main reason for permanent treatment discontinuation;
- Status at last study contact,

For all categories of patients (except for the non-randomized categories) percentages will be calculated using the number of randomized patients as the denominator.

Reasons for treatment discontinuation will be supplied in tables giving numbers and percentages by treatment group.

The incidence of premature treatment discontinuation (irrespective of the reason) and premature treatment discontinuation due to AEs will be presented graphically by treatment group on randomized and treated patients (as randomized), using Kaplan-Meier method.

All critical and major deviations potentially impacting efficacy analyses, randomization, and drug-dispensing irregularities, and other major deviations will be summarized in tables giving numbers and percentages of deviations by treatment group.

Additionally, the following populations will be summarized by treatment group. Definition of the study populations are provided in [Section 2.3](#).

- Randomized population
- Efficacy population: modified intent-to-treat (mITT) population/per-protocol population
- Safety population
- QOL population

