In EFC13672, alirocumab or placebo were administered Q2W for 52 weeks to 216 patients with hypercholesterolemia (including 41 patients with heFH) who were under treatment with statin and had not achieved the target LDL-C level. The administration was initiated with 75 mg and dose was up-titrated to 150 mg at Week 12 in the patients who did not achieve the target LDL-C level at Week 8. Among 140 patients who received alirocumab at Week 12 in the alirocumab group, 2 patients received up-titration. The least square (LS) mean differences versus placebo in the percent change in LDL-C from baseline to Week 12 and Week 24 were -61.5% and -64.1% respectively, showing that the statistically significant decrease was observed at Week 24 (primary

efficacy endpoint, $p < 0.0001$). The effect persisted up to Week 52 (LS mean present change from baseline in the alirocumab group, -62.5%).

Safety (EFC13672):

Alirocumab was well tolerated throughout the treatment period. Treatment-emergent adverse events (TEAEs) were reported in 90.9% of patients in the alirocumab group and 83.3% of patients in the placebo group. Ten patients (7.0%) in the alirocumab group and 9 patients (12.5%) in the placebo group experienced at least 1 treatment-emergent serious adverse event (SAE). There were no deaths reported. Seven patients (4.9%) in the alirocumab group and 4 patients (5.6%) in the placebo group experienced at least 1 TEAE leading to permanent investigational medicinal product (IMP) discontinuation.

Overall, 29 patients (20.3%) in the alirocumab group and 8 patients (11.1%) in the placebo group reported at least 1 TEAE that was considered by the Investigator to be related to the IMP. The most frequently reported TEAE considered to be related to the IMP was injection site reaction (18 patients [12.6%] in the alirocumab group and 3 patients [4.2%] in the placebo group). All the remaining TEAEs considered to be related to the IMP were reported in a single patient each.

Further details on alirocumab are provided in the Package Insert of Praluent®.

Rationale for protocol design in this study:

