10.3.3 List of criteria for permanent treatment discontinuation (SoC or IMP)

The patients may withdraw from study treatment if they decide to do so, at any time and irrespective of the reason, or this may be the Investigator's decision. Patient withdrawal from the study treatment or study should be avoided as much as possible. All efforts should be made to document the reasons for treatment discontinuation and this should be documented in the e-CRF.

Patients should discontinue the study treatment for the following reasons:

- Pregnancy, intention for pregnancy, or no longer taking an effective contraceptive method (in female patients).
- Acute injection-site reaction of clinical concern.

- SAE (or non-serious but severe in intensity) of hypersensitivity reaction considered to be related to study treatment.
- At patient's request.
- If, in the Investigator/sub-Investigator's opinion, continuation of the study treatment is detrimental to the patient's well-being.
- Condition that requires discontinuation of study treatment (e.g., laboratory abnormalities, refer to decision tree Appendix F).
- At the specific request of the Sponsor.
- At the specific request of the Investigator with Sponsor's agreement.

Criteria of permanent treatment discontinuation due to insufficient adherence to medications are defined as followed:

- Alirocumab arm: IMP administration compliance is less than 50% for 12 weeks (3 months from the randomization visit).
- SoC arm: NIMP administration compliance is less than 50% for 6 months from the randomization visit.

Note for SoC arm: If patients exhibit their NIMP administration compliance is less than 50% for the first 3 months after the randomization visit, Investigators/sub-Investigator can terminate the study based on their judgment considering patients' safety.

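### The AE-discontinuation curve uses Kaplan-Meier with no stated rule for patients who stop for other reasons; read in the usual way, it slightly overstates the incidence

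*SAP*

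**What the plan says.** SAP section 2.2 (Disposition of patients) plans two curves by arm. The first is described as "The incidence of premature treatment discontinuation (irrespective of the reason"). The second covers "premature treatment discontinuation due to AEs will be presented graphically by treatment group on randomized and treated patients (as randomized), using Kaplan-Meier method". The word incidence governs both. The section does not say when a patient is censored, or how a patient who stops for a reason other than an AE enters the second curve. Neither document mentions competing risks or a cumulative incidence function.

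The same section plans a table: "Reasons for treatment discontinuation will be supplied in tables giving numbers and percentages by treatment group". Its percentages are taken over randomized patients, whereas the curves use patients randomized and treated.

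Protocol section 10.3.2 defines permanent discontinuation as a definitive decision not to expose the patient to the study drug again. Section 10.3.3 lists grounds that need not involve an AE, among them the patient's request, pregnancy, a sponsor request and poor adherence. The adherence rule differs by arm: "Alirocumab arm: IMP administration compliance is less than 50% for 12 weeks (3 months from the randomization visit") against "SoC arm: NIMP administration compliance is less than 50% for 6 months from the randomization visit". A note adds that investigators may end participation for an SoC patient whose compliance is below 50% over the first 3 months.

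**The concern.** A patient who has permanently stopped for another reason cannot later stop because of an AE. For AE discontinuation, that earlier stop is a competing event. Ordinary censoring treats the patient as someone whose AE stop might still occur unobserved. One minus Kaplan-Meier then estimates how many would stop for AEs if nobody ever stopped for another reason. That is not the incidence the SAP names.

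The size of the excess depends on how many other-reason stops there are and when they fall. Two arms with the same AE discontinuation could therefore show slightly different curves. In an open-label trial this figure is a natural place for a reader to look for a tolerability difference. The curve for discontinuation for any reason is not affected, because every stop counts as an event.

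**Working it through.** The documents state no expected figure for either curve, so there is nothing of the plan's own to reproduce. The check compares one minus Kaplan-Meier, with other-reason stops censored, against the cumulative incidence.

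**Inputs**
- True AE discontinuation, *a*: 5%, with 10% as a higher case. The anchor is the Japanese phase 3 study in Protocol section 4: "Seven patients (4.9%) in the alirocumab group and 4 patients (5.6%) in the placebo group experienced at least 1 TEAE leading to permanent" discontinuation of study drug. That study ran 52 weeks against placebo. It is a guide only, not an assumption of this trial.
- Other-reason discontinuation, *o*: not given in either document. Assumed 5% to 20%, with 25% as an outer value.
- Cause-specific hazards constant over the treatment period (assumption).

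**Formula.** The total cumulative hazard is H = −ln(1 − a − o). Constant hazards split it in the ratio a : o, so the AE part is H × a/(a + o). Hence

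1 − KM = 1 − exp[−H × a/(a + o)] = 1 − (1 − a − o)^(a/(a + o)).

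The cumulative incidence function ends at *a*.

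**Results**

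| True AE stops | Other-reason stops | Calculation | 1 − KM | Excess (points) |
|---|---|---|---|---|
| 5% | 5% | 1 − 0.90^(1/2) | 5.13% | 0.13 |
| 5% | 10% | 1 − 0.85^(1/3) | 5.27% | 0.27 |
| 5% | 20% | 1 − 0.75^(1/5) | 5.59% | 0.59 |
| 10% | 20% | 1 − 0.70^(1/3) | 11.21% | 1.21 |

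With no other-reason stops the two estimators agree.

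**Between arms.** With 5% true AE stops in both arms, and other-reason stops of 5% in one and 20% in the other, the curves end at 5.13% and 5.59%. The spurious gap is 0.46 points.

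**Timing bounds.** Take 100 patients, 5 AE stops and 20 other-reason stops.
- All other-reason stops first: 80 remain at risk, so 1 − KM = 1 − 75/80 = 6.25%.
- All other-reason stops last: 1 − KM = 5/100 = 5.00%, with no excess.
- With 25 other-reason stops, all first: 5/75 = 6.67%, about 1.7 points too high.

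**What drives the excess.** Under constant hazards the ratio of 1 − KM to the true incidence depends almost only on *o*: about 1.03 at 5%, 1.06 at 10% and 1.12 at 20%, for AE rates from 2.5% to 10%. In absolute points it also rises with *a*. AE 10% with other 10% gives +0.56, but AE 3% with other 20% gives only +0.35.

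**Scale.** With about 100 patients per arm, one patient is 1 point. The standard error of a 5% proportion is √(0.05 × 0.95/100) = 2.2 points, and that of a difference is √2 times this, 3.1 points. The 0.46-point gap is about 0.15 of that standard error.

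**The case against.** The strongest reply is that the SAP never says other-reason stops are censored; it says only "using Kaplan-Meier method". If those patients were kept at risk to the planned end of treatment, the curve would equal the cumulative incidence. This is correct, and it means the text shows a missing rule rather than a stated wrong one. Censoring at the stop is still the ordinary reading, and nothing in the SAP points to the alternative.

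A reader might infer from the adherence rules that other-reason stops come earlier in the alirocumab arm and inflate its curve more. The documents do not support that. Adherence is one ground among several, no rate is given for any of them, and the SoC note allows a stop after 3 months. Nor does the arm with more other-reason stops always have the larger excess: in absolute points that also needs similar AE rates and similar timing.

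A reader might also blame Kaplan-Meier for any mismatch between the figure and the table of reasons. The denominators already differ (randomized and treated versus randomized), so a mismatch could remain after the estimator is changed.

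Finally, the figure is descriptive. Protocol section 11.4.3 rules out formal testing of safety data, and AE discontinuation is also reported as simple proportions in the SAP section 2.2 table of reasons and the SAP section 2.4.5.1 tables. This stands. It limits the weight of the point but does not make Kaplan-Meier the right estimator of incidence.

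**Conclusion.** The point holds as a minor one. For AE-related discontinuation the SAP names incidence as the target, chooses a method that does not estimate it when patients also stop for other reasons, and leaves the handling of those patients unstated. If they are censored, the curve is never below the cumulative incidence. Near 5% AE stops, with 5% to 20% other-reason stops, the excess is 0.1 to 0.6 points under constant hazards. It reaches about 1.7 points only if 25% of patients stop for other reasons before any AE stop.

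These sizes rest on assumed other-reason rates and on an AE rate borrowed from another study. The excess can differ between arms, but its direction cannot be predicted from the documents. The primary analysis, the key secondary analysis and the curve for discontinuation for any reason are unaffected.

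**What to change.** In SAP section 2.2, keep Kaplan-Meier for discontinuation for any reason. Present AE-related discontinuation as a cumulative incidence function (Aalen-Johansen) by arm, with discontinuation for any other reason as the competing event and completers censored at end of treatment. A footnote should explain the competing event, and should note that the curve uses randomized and treated patients while the table of reasons uses all randomized patients.

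The cost is about one sentence of SAP text, the footnote and a change of estimator in the program for one figure. No new data, change in sample size or protocol amendment is needed.

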### **2.2.1 Randomization irregularities**

Randomization irregularities occur whenever:

1. A randomization is not in accordance with the protocol-defined randomization method, such as, a) a patient is randomized based on an incorrect stratum, b) a patient is randomized twice,

Randomization irregularities will be monitored throughout the study and reviewed on an ongoing basis.

All randomization irregularities will be documented in the clinical study report. These irregularities will be summarized by treatment group on the randomized population. Non-randomized, treated patients will be described separately.

Randomization irregularities to be prospectively identified include but are not limited to:

Randomization irregularities
Patient randomized twice
Stratification error

## **2.3 ANALYSIS POPULATIONS**

Patients treated without being randomized will not be considered randomized and will not be included in any analysis population. The safety experience of patients treated and not randomized will be reported separately.

Randomized population: includes all randomized patients as defined in [Section 2.2](#).

For any patient randomized more than once, only the data associated with the first randomization will be used in any analysis population. The safety experience associated with any later randomization will be assessed separately.

### **2.3.1 Efficacy populations**

#### **2.3.1.1 *Modified intent-to-treat population***

The primary efficacy analysis population will be the modified intent-to-treat (mITT) population, defined as the randomized population who took at least one dose or part of dose of study drug, and has 2 analyzable normalized TAV, as defined below.

- One assessed before randomization
- Another one assessed after 24 weeks of treatment.

Patients in the mITT population will be analyzed according to the treatment group allocated by randomization.

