STATISTICAL CONSIDERATIONS	
Sample size determination: The study is expected to enroll approximately 200 patients. Based on the results of ZEUS(1) and PRECISE-IVUS(2) studies, it is assumed that difference in percent change in normalized TAV from baseline between alirocumab arm and SoC arm is 8%, and the common standard deviation of percent change in normalized TAV is 15%. Under the assumption, a sample size of 150 patients (75 in the alirocumab arm and 75 in the SoC arm) will have 90% power to detect the treatment difference with two-sided significance level of 5%. Assuming that proportion of non-evaluable primary endpoint is 25%, it is considered that 200 patients (100 in the alirocumab arm and 100 in the SoC arm) will be needed.
 
Analysis population: Randomized population includes all patients who have been allocated to a randomized treatment and recorded in the registration center database, regardless of whether a study drug was used or not. The primary efficacy analysis population will be the modified intent-to-treat (mITT) population, defined as the randomized population who takes at least one dose or part of dose of study drug and has an available value of normalized TAV before randomization and after 24 weeks of treatment. Patients in the mITT population will be analyzed according to the treatment arm allocated by randomization. The safety population consists of patients of randomized population who actually received at least one dose or partial dose of study treatment. The safety population will be analyzed according to the treatment actually received.
 
Primary analysis: The percent change in normalized TAV will be analyzed using an analysis of covariance (ANCOVA) model with treatment arm and randomization strata as fixed effects, and the baseline normalized TAV as covariate.
 
Analysis of Key secondary efficacy endpoints: Analysis of key secondary efficacy endpoint will be performed on the mITT population considering corresponding baseline value as covariate, in the same manner as for the primary endpoint.
 
Multiplicity adjustment: A hierarchical procedure will be used to control the type I error and to handle multiple endpoints. If the primary endpoint analysis is significant at the two-sided 5% alpha level, the key secondary

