1 FLOW CHARTS

1.1 GRAPHICAL STUDY DESIGN

Abbreviations: ACS, acute coronary syndrome; IC, informed consent; IVUS, intravascular ultrasound; LDL-C, low-density lipoprotein cholesterol; LMT, lipid modifying therapy; Q2W, every 2 weeks; R, randomization; SoC, standard of care.

- a If patients have not been on any statin therapy at ACS onset, either atorvastatin 10 mg/day or rosuvastatin 5 mg/day is started immediately after the ACS diagnosis.
- b At randomization, patients should have already received stable statin therapy with either atorvastatin ≥10 mg/day or rosuvastatin ≥5 mg/day for at least 2 weeks.
- c Stable dose statin monotherapy (atorvastatin ≥10 mg/day or rosuvastatin ≥5 mg/day within the range of statin doses approved by the Health Authority) will be administered to achieve the LDL-C target level <100 mg/dL. Concomitant non-statin LMTs will be considered if patients have already been on them on top of statin monotherapy at the time of ACS diagnosis or if LDL-C target level <100 mg/dL cannot be achieved by the statin monotherapy. Adjusting of LMT will occur based on above rule, but not limited.
- d Praluent® 75 mg Q2W on top of stable dose of atorvastatin ≥10 mg/day or rosuvastatin ≥5 mg/day ± other LMTs, in accordance with doses approved by the Health Authority. Concomitant non-statin LMTs will be considered if patients have already been on them on top of statin monotherapy at the time of ACS diagnosis. Background statin and/or non-statin LMT regimens should not be changed as a principle during the entire study period.
- e In the alirocumab arm, if LDL-C level at Week 12 measured by the central laboratory does not reach <100 mg/dL, Praluent® dose up-titration to 150 mg Q2W will be carried out at Week 14.
- f Patients who perform self-injection of Praluent® at home must visit the study site at least every 4 weeks, and at Week 0, Week 4, Week 12, Week 14, Week 24 and Week 36.

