10.1 VISIT SCHEDULE

Patients with hypercholesterolemia, who develop ACS and undergo successful therapeutic intervention such as PCI (stent placement), and IVUS imaging, are the target subjects of the current study. All patients have to have been received stable statin therapy with either atorvastatin ≥ 10 mg/day or rosuvastatin ≥ 5 mg/day for at least 2 weeks prior to the randomization visit (Visit 1).

Between the onset of ACS and the randomization visit (within 4 weeks prior to the randomization visit), the patient will receive verbal information concerning the aims and methods of the study, its constraints and risks, and the study duration, and will be provided of a written summary. The written informed consent must be signed by the patient and the Investigator prior to any study activity. Only patients who meet the inclusion/exclusion criteria as noted in [Section 7](#) will be enrolled to the study. Women of childbearing potential will be instructed to use a medically approved contraceptive method throughout the entire study period.

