11.3.1.1 Modified intent-to-treat population

The modified intent-to-treat population is the randomized population which takes at least one dose or part of dose of study drug and has an available value of normalized TAV before randomization, and after 24 weeks of treatment. Patients will be analyzed in the treatment arm to which they are randomized.

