### **2.3.2 Safety population**

The safety population considered for the safety analyses will be the randomized population who actually received at least 1 dose or part of a dose of the study drug (alirocumab or standard of care). Patients will be analyzed according to the treatment actually received (i.e. as-treated treatment group, Standard of Care or Alirocumab).

In addition:

- Non-randomized but treated patients will not be part of the safety population, but their safety data will be presented separately.
- Randomized patients for whom it is unclear whether they took the study drug will be included in the safety population as randomized.
- The treatment group allocation for “as-treated analysis” will be defined as follows:
  - Alirocumab group if IMP injection proportion is  $\geq 50\%$ .
  - SoC group if IMP injection proportion is  $<50\%$ .

IMP injection proportion (%) defined as  $100 \times (\text{Number of IMP injection}) / [(\text{the date of last study treatment administration} - \text{the date of randomization}) / 14 + 1]$

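### The mITT set requires a dose of study drug, undefined by arm, in an open-label trial; on one reading it can drop never-injected patients from the alirocumab arm only, and on the other it does almost nothing

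*SAP*

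**What the plan says.** The SAP's primary set is "defined as the randomized population who took at least one dose or part of dose of study drug, and has 2 analyzable normalized TAV", one image before randomization and one after 24 weeks of treatment, with patients analyzed as randomized (SAP 2.3.1.1). Protocol 11.3.1.1 has "the randomized population which takes at least one dose or part of dose of study drug", and the synopsis uses the same condition: "takes at least one dose or part of dose of study drug and has an available value of normalized TAV before randomization".

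Neither mITT definition explains *study drug*. The only explanation is in the safety population (SAP 2.3.2), which takes randomized patients who "received at least 1 dose or part of a dose of the study drug (alirocumab or standard of care"). The same section assigns patients for as-treated analysis by injections: "SoC group if IMP injection proportion is" below 50%, which includes zero.

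Three further facts matter:

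- **Knowledge of the arm.** Treatment is open-label and only the IVUS reading is blinded (protocol 8.3.1). The arm is communicated at the randomization visit, and the first injection follows at that visit (protocol 10.1.1.1, randomization visit).
- **Background statin.** Protocol 10.1 states: "All patients have to have been received stable statin therapy with either atorvastatin" or rosuvastatin, for at least 2 weeks beforehand. The note to protocol 1.1 agrees: "At randomization, patients should have already received stable statin therapy". SoC patients simply continue their lipid therapy.
- **Never-treated patients.** SAP 2.2 lists "Randomized but not treated patients and reason for not being treated" as a disposition category. SAP 2.1.2 and 2.4.5.2 also provide for patients who are randomized but not treated.

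**The concern.** Leaving out never-treated patients is usually harmless when the decision to start cannot depend on the allocated arm, as in a double-blind trial. Here it can. An alirocumab patient may decline the injection, or be judged unsuitable for it, after the allocation is known. An SoC patient has nothing new to start. A dose condition can therefore act on one arm only, and for a reason connected with knowing the arm, which is the kind of selection that randomization is meant to prevent.

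The condition also brings no evident benefit to the primary analysis. Two analyzable TAV values are required anyway, so patients without a late scan are already out in both arms. All that the dose condition can add is the removal of patients who have the outcome measured.

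**Working it through.** **1. What the condition does under each meaning of study drug**

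| Meaning | Alirocumab arm, never injected, statin continued, two images | SoC arm, two images | Net effect |
|---|---|---|---|
| Allocated treatment | Excluded | Kept | Can remove patients from one arm |
| Alirocumab or standard of care (SAP 2.3.2) | Kept, analyzed as randomized | Kept | Removes almost nobody; redundant |
| Alirocumab only | Excluded | Whole arm excluded | Cannot be intended |

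The randomized-but-not-treated categories favour the first meaning. SAP 2.1.2 classifies the medications of such patients, so a patient can be taking medication and still count as not treated. If background statin counted as a dose for everyone, the category would be nearly empty. SAP 2.3.2 favours the second. The mITT text does not settle it.

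**2. Can a never-injected patient have two images?** Yes. Baseline IVUS precedes randomization. The Week 36 window is any day from Day 169, counted from randomization (SAP 2.5.4.1, Table 3). Unscheduled IVUS may be used (SAP 2.5.5). Protocol section 4 describes follow-up angiography at 8 to 10 months as standard in Japan.

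**3. The plan's own figures** (protocol 11.1: difference 8, SD 15, two-sided 5%, 90% power). A two-sample t-test has power 89.7% with 74 per arm and 90.06% with 75, so 75 per arm reproduces. Allowing for 25% non-evaluable, 75 / 0.75 = 100 per arm. Nothing here is wrong, and the fix does not alter these numbers.

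**4. Size of the effect.** The documents give no rate of never-injected patients, so *d*, their share of the 75 evaluable alirocumab patients, is an assumption.

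Standard error of the difference: 15 × √(2/75) = 2.45.

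If never-injected patients gain no alirocumab benefit, the all-randomized difference is 8 × (1 − d), so excluding them raises the estimate by 8 × d. At 1% this is 8 × 0.01 = 0.08 points and at 3% it is 8 × 0.03 = 0.24 points. The larger is 0.24 / 2.45, about one tenth of a standard error.

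Power, by two-sample t-test, with these patients kept (75 v 75, difference 8(1 − d)) and excluded (75 v 75(1 − d), difference 8):

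| d | Difference if kept | Power if kept | Power if excluded |
|---|---|---|---|
| 1% | 7.92 | 89.5% | 89.9% |
| 2% | 7.84 | 88.9% | 89.8% |
| 5% | 7.60 | 86.9% | 89.3% |
| 10% | 7.20 | 83.2% | 88.4% |

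**5. Type I error from one-arm exclusion.** Suppose alirocumab has no effect and the excluded patients differ from the rest by *g* points. The difference between arms then shifts by d × g.

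| d | g = 8: shift, type I error | g = 15: shift, type I error |
|---|---|---|
| 1% | 0.08, 5.0% | 0.15, 5.0% |
| 2% | 0.16, 5.1% | 0.30, 5.2% |
| 5% | 0.40, 5.3% | 0.75, 6.0% |
| 10% | 0.80, 6.2% | 1.50, 9.1% |

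The inflation becomes noticeable only when both the share and the prognostic gap are large.

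**The case against.** The strongest objection is that one-arm exclusion is not established. A reader might infer that patients who decline alirocumab are certainly dropped while every SoC patient qualifies automatically. That takes study drug in the wide sense for one arm and in a narrower sense for the other. Alirocumab patients take the same background statin, and under SAP 2.3.2 one who declines injections but continues it has arguably taken study drug. The as-treated rule, which puts zero injections with SoC, fits that view. Nor does any section say that statin taken before randomization counts as a dose. This stands: exclusion is one reading of an undefined term, though the better supported one.

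Second, the dose condition may not be the only obstacle. Protocol 9.1.1 and SAP 2.1.3 and 2.1.3.1 require the late image to follow at least 24 weeks of treatment. If treatment means injections, a never-injected patient fails there too. This stands, and the fix has to cover it.

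Third, numbers should be few. Eligibility is confirmed before the arm is disclosed, the first injection is given at the same visit, and protocol 10.3.4 arranges a rescheduled evaluation IVUS only for discontinuation at or after Week 24. This also stands.

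Fourth, SAP 2.4.4.1 plans a multiple-imputation analysis on the randomized population, where a never-injected patient with two images enters with observed values. That is real mitigation, but partial. It changes the patient set and the missing-data method together, so it cannot isolate this exclusion. The SAP names the primary analysis as the main result, and the key secondary test depends on it (SAP 2.4.4.3).

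A reader might also infer that each exclusion costs precision. Under the no-benefit assumption the reverse holds: power is slightly higher with these patients excluded.

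**Conclusion.** The concern holds as a defect of definition with a small expected effect. The primary set conditions on an event after randomization, in a trial where the arm is known before that event, through a term not defined by arm. If the term means the allocated treatment, the condition can realistically remove patients from the alirocumab arm only. If it means alirocumab or standard of care, it is redundant. On neither reading does it help the primary analysis.

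At an assumed 1 to 3% never injected but imaged, and no benefit in those patients, the shift is 0.08 to 0.24 points against a standard error of about 2.4. Type I error stays at or below 5.2% for shares of 1 to 2%, even with a 15-point prognostic gap; it reaches 9.1% only at 10% with that gap. The documents do not support saying that the primary result will be biased to an important degree. The asymmetry is clear; how the condition would be applied is uncertain.

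**What to change.** - Delete the dose condition from the mITT definition in SAP 2.3.1.1, protocol 11.3.1.1 and the synopsis.
- Define the primary set as all randomized patients with an analyzable normalized TAV before randomization and one in the Week 36 window (Day 169 or later, counted from randomization), analyzed as randomized.
- Align the 24-weeks-of-treatment wording in protocol 9.1.1 and SAP 2.1.3 and 2.1.3.1 with that window. Otherwise the same patients could still be lost through the endpoint definition.
- Report by arm the patients who never started their allocated treatment (in the alirocumab arm, never injected) and how many of them have two analyzable images.
- Keep the dose condition for the safety set.

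The cost is a few lines in the SAP and a matching protocol clarification, with no new data and no change to the planned 200 patients. It should be settled before database lock. The downside is that, if never-injected patients gain no benefit, the expected difference and the power fall slightly, for example to 89.5% rather than 89.9% at a 1% share.
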